9.3.1.1. Statistical Evaluation of Safety

Safety parameters that will be assessed include safety laboratory parameters, vital signs, and ECG parameters. Additional analysis will be performed if warranted upon review of the data.

9.3.2. Pharmacokinetic Analyses

9.3.2.1. Pharmacokinetic Parameter Estimation

Pharmacokinetic parameter estimates will be calculated by standard noncompartmental methods. The primary PK parameters for analysis of selpercatinib will be: C_{max} , $AUC(0-\infty)$, $AUC0-t_{last}$, and t_{max} .

Other noncompartmental parameters, such as $t_{1/2}$, apparent total body clearance of drug calculated after extravascular administration, and apparent volume of distribution during the terminal phase after extravascular administration, may be reported as appropriate.

9.3.2.2. Pharmacokinetic Statistical Inference

Pharmacokinetic parameters will be evaluated to estimate bioequivalence. For the primary analysis, log-transformed C_{max} , $AUC0-t_{last}$, and $AUC(0-\infty)$ will be evaluated in a linear mixed-effect model with fixed effects for formulation, period, and sequence, and a random effect for subject. The treatment differences will be back-transformed to present the ratios of geometric means and the corresponding CIs.

For secondary analysis, the t_{max} will be analyzed using a Wilcoxon signed rank test. Estimates of the median difference based on the observed medians, 90% CIs, and p-values from the Wilcoxon test will be calculated. Pharmacokinetic parameters will be summarized using descriptive statistics.

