4.2. Scientific Rationale for Study Design

A single 160-mg dose of selpercatinib was selected as it is the highest proposed dose for selpercatinib use in adults.

In order to allow each participant to act as his/her own control for safety and PK comparisons, a 2-sequence, 2-period crossover design has been selected. This study will also be open-label as the study primary endpoint PK measures are objective rather than subjective.

The two-stage adaptive design will be used because assumption of intrasubject variability for C_{max} is not well established. Stage 1 PK results will be used to determine intrasubject variability for C_{max} and AUC and the required sample size for Stage 2. Potvin Method C (Potvin 2007) will be used to control the one-sided type I error rate ($\alpha=0.05$) for assessing bioequivalence in 2 stages. (See details in Section 9.4).

Conducting the study in healthy participants mitigates the potential confounding effects of the disease state and concomitant medications in participants with metastatic RET fusion-positive NSCLC, advanced or metastatic RET-mutant MTC, or advanced or metastatic RET fusion-positive thyroid cancer. A population of healthy participants is frequently used in the assessment of the PK of both small and large molecules.

Selpercatinib has pH-dependent solubility, with decreasing solubility at higher pH; exploratory analysis of pH measurements via NG tube placement, aspiration of gastric secretions and tested on a pH meter will be included in Stage 1 to understand the pH dynamics, including the potential of pH effect on absorption. The pH will not be measured in Stage 2 of the study. Stage 1 is sufficiently sized to ensure that within these normal healthy participants a sufficient range of pH will be detected for the planning of Stage 2 which is planned to fulfill the bioequivalence (BE) guidance for change of delivery option.

The doses, participant population, study duration, and sample collection timing are considered adequate to achieve the study objectives.

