9.5. Sample Size Determination

The incidence of those participants with a different PK profile (2 of 19 subjects in Study LOXO-RET-18015) has meant that Lilly is planning to enroll up to approximately 60 participants in Stage 1. This is to ensure that at least 50 participants will complete Stage 1 and a sufficient variation of gastric pH will be incorporated in Stage 1.

If the true intraparticipant CV is 30% for C_{max} and 20% for AUC, the first 50 participants in Stage 1 will give approximately 90% power to meet BE criteria at a 1-sided α level of 0.05, under an assumption of a GMR of 1.05.

Table JZJZ.9.1 shows the required sample size for Stage 2 to provide the power for C_{max} of 90% based on different intrasubject CV for C_{max} from Stage 1, assuming the true tablet-to-capsule GMR is 1.05 under scenario when the power is less than 90% and BE is not met at Stage 1. The actual sample size for Stage 2 will be determined based on the observed intrasubject CV at Stage 1.

In Stage 1, dropouts will not be replaced.

In Stage 2, dropouts will not be replaced, but over-enrollment of up to 20% of the determined sample size will be permitted to ensure a sufficient number of participants.

Table JZJZ.9.1. Sample Size for Stage 2 Based on Intrasubject CV for C_{max} in Stage 1

Intrasubject CV for C_{max} in Stage 1	Required Sample Size for Stage 2
40%	50
50%	100
60%	156
70%	216

Abbreviations: C_{max} = maximum serum concentration; CV = coefficient of variation.

Note: The total sample size will be at least 50 for Stage 1 plus the required sample size for Stage 2.

10. Supporting Documentation and Operational Considerations

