3. INTRODUCTION

This SAP has been developed after review of the Clinical Study Protocol (final version dated 19 July 2021), Protocol Amendment (a) (final version dated 04 August 2021), Protocol Amendment (b) (final version dated 13 August 2021), and Protocol Amendment (c) (final version dated 14 October 2021).

This SAP describes the planned analysis of the safety, tolerability, pharmacokinetic (PK) and pharmacodynamic (PD) data from this study. A detailed description of the planned TFLs to be presented in the clinical study report (CSR) is provided in the accompanying TFL shell document.

The intent of this document is to provide guidance for the statistical and PK analyses of data. In general, the analyses are based on information from the protocol, unless they have been modified by agreement with Eli Lilly and Company. A limited amount of information concerning this study (e.g., objectives, study design) is given to help the reader's interpretation. For open-label studies, this SAP must be signed off prior to first participant visit for this study. When the SAP and TFL shells are agreed upon and finalized, they will serve as the template for this study's CSR.

This SAP supersedes the statistical considerations identified in the protocol; where considerations are substantially different, they will be so identified. If additional analyses are required to supplement the planned analyses described in this SAP, they may be performed and will be identified in the CSR. Any substantial deviations from this SAP will be agreed upon with Eli Lilly and Company and identified in the CSR. Any minor deviations from the TFLs may not be documented in the CSR.

This SAP is written with consideration of the recommendations outlined in the International Conference on Harmonisation (ICH) E9 Guideline entitled Guidance for Industry: Statistical Principles for Clinical Trials¹ and the ICH E3 Guideline entitled Guidance for Industry: Structure and Content of Clinical Study Reports².

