9.3.2 Pharmacokinetic Statistical Methodology

PK parameters will be evaluated to estimate BE of the selpercatinib tablet and capsule formulations.

For the primary analysis, log-transformed C_{\max} , $AUC(0-t_{last})$, and $AUC(0-\infty)$ parameters will be evaluated in a linear mixed effect model with fixed effects for treatment formulation, period, sequence, and a random effect for participant. The differences between the tablet (test) and capsule (reference) formulations will be back-transformed to present the ratios of geometric least squares means and the corresponding CIs. Intra-participant CV will be derived and bioequivalence will be met if the CI for the ratio falls within 80%-125%.

CCI

CCI

CCI

CCI

CCI

CCI
CCI
CCI
CCI

For secondary analysis, the t_{max} will be analyzed using a Wilcoxon signed rank test. Estimates of the median difference based on the individual paired differences, CIs, and p-values from the Wilcoxon signed rank test will be calculated.

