11. CHANGES FROM THE PROTOCOL SPECIFIED STATISTICAL ANALYSES

There were no changes from the protocol specified statistical analyses.

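### The secondary t_max test ignores period, and its estimator changed between protocol and SAP without being declared: small effect, BE decision untouched, near-free to fix

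*Protocol*

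**What the plan says.** Protocol 4.2 states that "a 2-sequence, 2-period crossover design has been selected". For log-transformed C_max and AUC, protocol 9.3.2.2 specifies a "linear mixed-effect model with fixed effects for formulation, period, and sequence, and a random effect for subject", and SAP 9.3.2 has the same model.

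For t_max, protocol 9.3.2.2 says "For secondary analysis, the t_{max} will be analyzed using a Wilcoxon signed rank test", and the SAP names the same test. Neither visible text adjusts that test for period or sequence.

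The two documents describe the estimate that goes with the test differently:
- Protocol 9.3.2.2: "Estimates of the median difference based on the observed medians, 90% CIs, and p-values from the Wilcoxon test will be calculated".
- SAP 9.3.2: "Estimates of the median difference based on the individual paired differences, CIs, and p-values from the Wilcoxon signed rank test will be calculated".

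SAP section 3 sets the precedence: "This SAP supersedes the statistical considerations identified in the protocol; where considerations are substantially different, they will be so identified". SAP section 11 then reports: "There were no changes from the protocol specified statistical analyses".

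On completers, protocol 9.5 says "In Stage 1, dropouts will not be replaced". About 60 are to be enrolled so that at least 50 complete Stage 1.

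**The concern.** In a 2x2 crossover each participant's tablet-minus-capsule difference contains the period effect, with opposite signs in the two sequences. The primary model removes it; a one-sample signed rank test on the pooled differences does not. With equal sequences the period effect is counted as noise, so the test rejects too rarely. With unequal sequences part of it remains in the estimated shift.

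Separately, a difference between two observed medians and an estimate built from paired differences are not the same quantity. A reader comparing the study report with the protocol would find a different estimator, and a CI whose level the visible SAP text does not fix, with nothing in the SAP to flag the change.

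At stake is the quality of a secondary description of absorption rate, for which a p-value and a CI are planned. Protocol 9.3.2.1 lists t_max among the primary PK parameters, but 9.3.2.2 places its analysis outside the primary analysis.

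**Working it through.** **Plan's own figures.** The documents give no power, margin or effect size for t_max. Their one Stage 1 power figure is about 90% at n = 50, with GMR 1.05, one-sided alpha 0.05, and CV 30% for C_max and 20% for AUC. It reproduces: 89.8% for C_max and 99.6% for AUC. It does not bear on t_max.

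**Algebra.** Let tau be the formulation shift and pi the period-2-minus-period-1 effect. The tablet-minus-capsule difference has centre tau + pi in the capsule/tablet sequence and tau − pi in the tablet/capsule sequence. With n1 and n2 completers, the pooled mean difference is tau + pi(n1 − n2)/(n1 + n2). For pi = 0.5 h:
- 25:25 gives 0.5 × 0/50 = 0
- 27:23 gives 0.5 × 4/50 = 0.04 h
- 30:20 gives 0.5 × 10/50 = 0.10 h

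Period-2-minus-period-1 differences have centres pi + tau and pi − tau. Comparing them between sequences cancels pi and estimates 2·tau, hence the halving.

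**Simulation inputs.** From the documents: median t_max 2 h (protocol 2.2), the sampling times in protocol 1.3, and n = 50. Assumed: lognormal t_max with between-participant log-SD 0.25 and within-participant log-SD 0.35, effects added in hours, a true shift of 0.5 h for power, and a two-sided 5% test. There were 2,000 to 3,000 runs per case (Monte Carlo error about 0.4 to 0.9 points).

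Power at 25:25 (ranges are over repeat runs):

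| Period effect | Signed rank | Period-adjusted rank-sum |
|---|---|---|
| 0 | 86–88% | 88–89% |
| 0.25 h | 86.7% | 88.3% |
| 0.5 h | 81–83% | 88–89% |
| 1.0 h | 63–65% | 87–88% |

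Type I error, signed rank (period-adjusted test where computed):
- 25:25, 0.5 h: 3.2% (5.0%)
- 27:23, 0.5 h: 3.0 to 3.6%; at 1.0 h: 1.9%
- 30:20, 0.25 h: 5.2%
- 30:20, 0.5 h: 6.5 to 7.1% (4.8 to 5.7%)
- 30:20, 1.0 h: 9.2% (4.9%)

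**Sensitivity.** A second model used multiplicative effects and within-participant log-SD 0.25, 0.35 and 0.50, with 1,500 runs per case. A period effect of 0.2 log units is 2 × (e^0.2 − 1) = 0.44 h, and 0.3 is 0.70 h. At 25:25 the signed rank test lost 3.5, 4.7 and 2.0 points of power at 0.44 h, and 9.8, 10.8 and 6.1 points at 0.70 h. At 30:20 its type I error was 5.8 to 8.3%, against 4.5 to 6.1% adjusted.

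**Estimators.** Take tablet values 1, 2, 3, 4, 6 and capsule values 2, 3, 1, 1.5, 2.5. The medians are 3 and 2, a difference of 1.0 h. The paired differences are −1, −1, 2, 2.5, 3.5, with median 2.0 h and Hodges-Lehmann estimate 1.25 h. So the protocol and SAP wordings differ, and the SAP wording still admits two estimators. In the hours-scale simulation the difference of medians and the median of paired differences disagreed in 31 to 57% of trials. The mean absolute gap was only 0.11 to 0.21 h, and it exceeded 0.5 h in at most 1.6% of trials.

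**CI level.** The design uses alpha 0.05 and 0.0294. The SAP's unqualified CI could therefore be 1 − 2 × 0.05 = 90% or 1 − 2 × 0.0294 = 94.12%.

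**The case against.** The case against has weight:

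- **No decision depends on t_max.** Protocol 9.4 and SAP 10 decide bioequivalence on AUC and C_max. This stands.
- **The SAP governs.** A reader might infer that the t_max estimate is undefined, or depends on which document is followed. Section 3 of the SAP does not support that: the paired-difference basis applies, and it suits a signed rank test. What remains open is the choice between sample median and Hodges-Lehmann, the CI level, and the section 11 statement. Section 3 asks only for substantial differences to be identified, and whether this one qualifies is a judgement. Blacked-out lines precede the t_max sentence in SAP 9.3.2 and may hold detail.
- **The period effect is assumed.** Within a stage, both periods share the same fast, water limits, dosing conditions and tube procedure. A washout of 14 days is 14 × 24/32 = 10.5 half-lives, so carryover is not a plausible source. An effect of 1.0 h would be half the 2 h median. This stands.
- **Marked imbalance is unlikely.** A reader might infer that any uneven dropout biases the shift or inflates type I error. The results do not support this: at 27:23 the test stays below 5%, and the 0.5 h effect moves the mean difference by only 0.04 h. If 60 were allocated 30:30 (the text states no ratio), 30:20 needs all 10 dropouts in one sequence. Under random dropout that has probability 2 × C(30,10)/C(60,10) = 0.08%. Protocol 7.2 also expects discontinuation to be uncommon.

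The argument that choosing the test is mere preference does not stand. The adjusted test loses nothing at 25:25 without a period effect, and keeps its size and power when there is one.

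**Conclusion.** The point holds as a minor improvement. The t_max test omits a design factor that the primary model includes. With balanced sequences and a period effect, the cost is conservatism and lost power: about 1 to 2 points at 0.25 h, 5 to 7 at around 0.5 h, and over 20 only at 1.0 h. Type I error exceeds nominal only with both marked imbalance and a sizeable period effect, at about 6.5 to 7% for 30:20 and 0.5 h. With no period effect there is no harm.

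The change of estimator and the dropped 90% level are visible in the text and need no assumption; the SAP's no-changes statement does not reflect them. The numerical consequence is small, about 0.1 to 0.2 h on average.

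These sizes rest on the assumed t_max distribution, period effect and sequence split. They also rest on t_max taken at nominal sampling times, whereas SAP 9.3.1 uses actual times, which would change how often the estimates differ. Nothing here supports doubt about the bioequivalence conclusion.

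**What to change.** In SAP 9.3.2, replace the signed rank test for t_max with a Wilcoxon rank-sum test on each participant's period-2-minus-period-1 difference, compared between the two sequences. Report half the Hodges-Lehmann shift between sequences, signed as tablet minus capsule, with its 90% CI. List the test, estimator and CI level in SAP 11 as a change from protocol 9.3.2.2.

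If the signed rank test is kept, the minimum is to name one estimator and its CI level and record the difference in SAP 11.

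Stratifying by stage, should Stage 2 run, is optional; the visible primary model has no stage term either.

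The cost is a few lines of SAP text and code, with no new data. Power is unchanged at balanced sequences. At 30:20 with no period effect, the adjusted test gave up about 1 to 2.5 points in the log-scale simulations (for example 74.1% v 72.8%).

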9.3.3. Pharmacodynamic Analyses

The pH data will be listed and summarized using descriptive statistics.

9.3.4. Pharmacokinetic/Pharmacodynamic Analyses

Not applicable for this study.

9.4. Interim Analysis

At completion of Stage 1, an interim analysis will be conducted to test BE and estimate the power before continuing to Stage 2.

In order to meet the BE criterion at a specific α level, the 2-sided confidence interval for the tablet-to-capsule (tablet formulation / capsule formulation) geometric mean ratio (GMR) for

AUC and C_{max} at the $(1-2\alpha)$ level should fall within 80%-125%. The sequential design approach of Potvin's Method C will be used to preserve the overall type I error rate at the 1-sided significance level of 0.05.

The BE testing and alpha spending scheme is described in [Figure JZJZ.9.1](#). At an interim analysis, the power will be evaluated using the intrasubject CV from Stage 1 using α level of 0.05 assuming the true tablet-to-capsule GMR is 1.05. If Stage 1 has at least 90% power, BE will be tested at Stage 1 at an α level of 0.05. The study will be stopped whether BE is met or not met. The evaluation of the power at Stage 1 will be based on C_{max} , which has higher variability. If the power is less than 90%, BE will be tested at an α level of 0.0294 as originally proposed by Pocock (Pocock 1977). If the BE criterion is met, the study will be stopped. If the BE criterion is not met, the sample size for Stage 2 will be calculated based on the intrasubject CV at Stage 1 and an α level of 0.0294 assuming the true tablet-to-capsule GMR is 1.05, and Stage 2 will be initiated. At Stage 2, BE will be evaluated using data from both stages at an α level of 0.0294.

[figure not shown]

Figure JZJZ.9.1. Adaptive sequential design method C (Potvin, 2007).

The Statistical Analysis Plan will describe the planned interim analyses in greater detail.

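### With α 0.0294 the two-stage rule lets the C_max type I error peak at about 5.05% (about 5.12% if all over-enrolled participants complete), so the stated 5% control is narrowly missed; α 0.0286 restores it at almost no cost

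*Protocol*

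**What the plan says.** Protocol section 9.4 sets the interim rule, and SAP section 10 repeats it.

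- Claim: "Method C will be used to preserve the overall type I error rate at the 1-sided significance level of 0.05".
- Gate passed: "If Stage 1 has at least 90% power, BE will be tested at Stage 1 at an α level of 0.05", after which the study stops whatever the result.
- Gate failed: "If the power is less than 90%, BE will be tested at an α level of 0.0294 as originally proposed by Pocock".
- If BE is then not shown, Stage 2 is sized from the Stage 1 CV at "an α level of 0.0294 assuming the true tablet-to-capsule GMR is 1.05, and Stage 2 will be initiated".
- Final look: "At Stage 2, BE will be evaluated using data from both stages at an α level of 0.0294".
- Driver of the gate: "The evaluation of the power at Stage 1 will be based on C_{max} , which has higher variability".

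Protocol section 9.5 and SAP section 7 add a 90% power target for Stage 2, at least 50 Stage 1 completers from about 60 enrolled, and a planning CV of 30% for C_max and 20% for AUC. Stage 2 dropouts are not replaced, but "over-enrollment of up to 20% of the determined sample size will be permitted to ensure a sufficient number of participants". The PK population (Protocol section 9.2, SAP section 8) takes every dosed participant with evaluable PK data. Nothing readable limits the pooled test to the determined Stage 2 number.

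**The concern.** Whether a fixed constant such as 0.0294 holds 5% depends on the rest of the rule: the power gate, the re-sizing target, the assumed GMR, the Stage 1 size, and how large Stage 2 becomes relative to Stage 1. The readable text shows no calculation for this combination and does not say how over-enrolment enters the error rate.

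Control at 5% is the property that supports a BE claim from pooled data. Protocol section 4.2 gives poorly established C_max variability as the reason for the adaptive design, so control should hold over the whole range of CVs that the plan allows for, not only at 30%.

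**Working it through.** **1. Reproduce the plan's figures.** For a balanced 2×2 crossover on the log scale, s² = ln(1+CV²) and SE = √(2s²/n), with n−2 df. BE is met if the estimate ± t·SE lies within ±ln 1.25 = ±0.2231.

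Stage 1 with n = 50, CV 30%, GMR 1.05, α 0.05:
- s² = ln 1.09 = 0.0862, and SE = √(0.1724/50) = 0.0587.
- (0.2231 − 0.0488)/0.0587 = 2.97. Subtracting t = 1.677 leaves 1.29, so power is about 90%. Exact integration over the variance gives 89.8%. The plan says approximately 90%.

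Stage 2 at α 0.0294 and 90% power, for CV 40/50/60/70%: 51/101/157/217 in steps of one, or 52/102/158/218 in even numbers. The plan tabulates 50/100/156/216, and power at those sizes is 89.9% to 90.0%. The sizing is reproduced within 2 participants.

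**2. Simulate the rule at the BE margin.** The true C_max ratio is 1.25. Draw the Stage 1 estimate and variance, apply the 90% gate at α 0.05 and GMR 1.05, and test at 0.05 or 0.0294 accordingly. If BE is not shown in the 0.0294 branch, size Stage 2 for 90% power and pool both stages with a stage term (N−3 df). Type I error in %, shown as determined size / all of 20% over-enrolment completing:

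| True C_max CV | 50 Stage 1 completers | 60 Stage 1 completers |
|---|---|---|
| 30% | 4.75 / 4.81 | 4.93 / 4.94 |
| 42% | 4.96 / 5.05 | 4.78 / 4.88 |
| 44% | 5.01 / 5.10 | 4.86 / 4.96 |
| 47% | 5.05 / 5.12 | 4.97 / 5.05 |
| 50% | 5.00 / 5.06 | 5.03 / 5.11 |
| 52% | 4.91 / 4.96 | 5.05 / 5.12 |
| 54% | 4.78 / 4.82 | 5.04 / 5.10 |
| 60% | 4.19 / 4.20 | 4.78 / 4.80 |
| 70% | 3.31 / 3.31 | 3.82 / 3.83 |

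Rows 42% to 54%, and 30% with 50 completers, use 600,000 stratified draws with the last probability integrated analytically. The other entries use 3 million plain trials (standard error about 0.013 points). With 60 completers and full over-enrolment, the plain run is still 5.05% at CV 56% and falls to 4.96% at 58%.

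Checks:
- 12 million plain trials at 50 completers and CV 46%: 5.04% and 5.13% (standard error 0.006).
- No stage term: 5.04% and 5.12%.
- AUC also required to pass (AUC GMR 1.00 to 1.05, CV 20%): 5.03–5.05% and 5.09–5.14% (standard error 0.013).
- AUC at the margin in place of C_max: about 4.7% or less.

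**3. Why there is a hump.** At low CV the gate usually passes and there is one test at 0.05. At high CV the Stage 1 interval is too wide to pass, so there is in effect one test at 0.0294. In between, both looks count, and their correlation is √(n1/N). With n1 = 50 it is √(50/100) = 0.71 when Stage 2 is 50, √(50/150) = 0.58 when it is 100, and √(50/170) = 0.54 when 100 becomes 120. Lower correlation gives more chance of a false positive at one look or the other, so completed over-enrolment raises the error.

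**4. Repeat with α 0.0286** (CI level 1 − 2×0.0286 = 94.28%).
- Maximum error for CV 42% to 54%: 4.92% as sized and 4.99% with full over-enrolment. The maximum over the whole grid is 5.00%, at low CV where Stage 1 is tested once at 0.05.
- Stage 2 in even numbers: 52/102/158 unchanged; CV 70% goes from 218 to 220.
- Overall power at GMR 1.05, no over-enrolment: CV 40%, 91.24% to 91.22%; CV 50%, 90.57% to 90.54%.
- Expected total size: CV 40%, 73.9 to 74.6 (0.7/73.9 = 0.9%); CV 50%, 125.1 to 126.7 (1.6/125.1 = 1.3%).
- Stage 1 power with n = 50 at the branch's α: CV 30%, 84.3% to 84.0%; CV 40%, 57.2% to 56.6%.

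**The case against.** The strongest reply is that an excess of 0.05 to 0.12 points, at a true ratio exactly on the margin and in a band about 10 CV points wide, is negligible, and that Method C is a named published approach. The small size is accepted. What remains is that the plan states control as a fact and that this exact rule does not quite deliver it, by far more than simulation error.

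A reader might infer that 5.12% is the plan's error rate. The documents do not support that. Over-enrolment is there because Stage 2 dropouts are not replaced. On the Stage 1 planning ratio of 50 completers from 60 enrolled, 1.20 × 50/60 = 1.00, which is the determined size, so about 5.05% is the more natural figure and 5.12% is the no-dropout extreme.

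A reader might also infer that the error exceeds 5% wherever Stage 2 is used. It does not. With 50 completers it is below 5% at three of the four tabulated CVs (40%, 60% and 70%), and also at 30%, where about half of trials fail the gate.

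Nor can one conclude that no supporting simulation exists. Both decision figures are not shown and part of SAP section 9.3.2 is redacted. The error rate here follows from the readable rule and does not depend on what is hidden.

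**Conclusion.** The point holds as a small one. Under the stated rule the maximum type I error for C_max is about 5.05% at the determined Stage 2 size and about 5.12% if all 20% over-enrolment completes, for a true CV of about 42% to 53% (up to about 56% with 60 Stage 1 completers). Outside that band it is at or below 5%.

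This rests on balanced sequences, log-normal data, a true C_max ratio of 1.25, Stage 2 rounded up to an even number, and AUC comfortably within the limits. It does not show that the sizing is wrong, since the plan's power and table are reproduced, or that a BE conclusion from this study would be unsafe. It is a desirable correction, not an essential one.

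**What to change.** Before any Stage 1 PK results are seen, replace 0.0294 by 0.0286 in Protocol section 9.4 and SAP section 10, at both looks of the two-stage branch and in the Stage 2 size calculation. Keep 0.05 where the gate is passed. Restate the Stage 2 table and file the simulation with the SAP.

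The cost is one constant, a short appendix, and a departure from the constant the plan cites. Intervals in that branch widen by about 0.6%. Against the even-number sizes reproduced at 0.0294, only the CV 70% row changes, by 2. The plan's printed sizes run about 2 lower than those and would give 89.7% to 89.8% power at 0.0286. Overall power moves by less than 0.1 point, expected total size rises by about 1%, and Stage 1 power in that branch falls by under 1 point.

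If 0.0294 is kept, replace the claim of preservation with the simulated maximum: about 5.05% as sized and about 5.12% with full over-enrolment. Do not cap the pooled analysis by dropping surplus Stage 2 completers. That would discard evaluable PK data, contradict the PK population in Protocol section 9.2 and SAP section 8, and still leave about 5.05%.

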2.3. Benefit/Risk Assessment

There is no anticipated therapeutic benefit for the healthy participants in this study. However, participants may benefit from the screening procedures (through detection of unknown health issues) even if they receive no therapeutic benefit from the study.

The dose of selpercatinib to be given in this study is 160 mg, as it is the highest approved dose. The safety profile of selpercatinib is very well tolerated in healthy volunteers and is clinically manageable, with the low rates of study drug discontinuation due to AEs.

As outlined in the IB, the most common toxicities associated with selpercatinib in patients are monitorable and reversible and include dry mouth, diarrhea, hypertension, fatigue, constipation, AST/ALT elevation, headache, nausea, edema peripheral, abdominal pain, rash, electrocardiogram QT prolonged, cough, vomiting, dyspnea and increased blood creatinine. Events of special interest include hypersensitivity, liver-function test abnormalities, thrombocytopenia, and hypertension. None of these events of special interest have been observed to date in healthy participants.

More detailed information about the known and expected benefits and risks and reasonably expected AEs of selpercatinib may be found in the IB.

3. Objectives and Endpoints

Objectives	Endpoints
Primary	

 To evaluate the bioequivalence of a single 160-mg dose of selpercatinib as the tablet formulation (test) compared to the commercial capsule formulation (reference) 	
 C_{max}, $AUC(0-\infty)$, and $AUC_{0-t_{last}}$ of selpercatinib
Secondary	

 To describe the safety and tolerability of a single 160-mg oral dose of selpercatinib as the tablet formulation (test) compared to the commercial capsule formulation (reference) 	
 Summary of the number of treatment-emergent AEs and serious adverse events
Exploratory	

 To determine whether the PK of selpercatinib are altered by initial pH 	
 C_{max}, $AUC(0-\infty)$, and t_{max} of selpercatinib

4. Study Design

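### Cheap improvement: Stage 2 follows any under-powered Stage 1 that fails BE, whatever the observed ratio; a confidence-interval futility stop would cost almost no power

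*Protocol*

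**What the plan says.** Protocol 9.4 and SAP 10 describe the same decision path under Potvin's Method C, which "will be used to preserve the overall type I error rate at the 1-sided significance level of 0.05".

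- Adequate power: "If Stage 1 has at least 90% power, BE will be tested at Stage 1 at an α level of 0.05", and the study then ends either way.
- Inadequate power: "If the power is less than 90%, BE will be tested at an α level of 0.0294 as originally proposed by Pocock". A pass ends the study. After a failure, Stage 2 is sized from the Stage 1 CV at α 0.0294, "assuming the true tablet-to-capsule GMR is 1.05, and Stage 2 will be initiated".
- Final analysis: "At Stage 2, BE will be evaluated using data from both stages at an α level of 0.0294".

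The power check uses one parameter: "The evaluation of the power at Stage 1 will be based on C_{max} , which has higher variability". The BE criterion itself covers AUC as well as C_max.

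The visible text of both documents has no condition on the observed ratio or its interval, no futility branch and no cap on Stage 2 size. The decision figure is not shown and part of SAP 9.3.2 is redacted, so this reading rests on the visible text. Protocol 10.1.7 lets the sponsor terminate the study at any time at its own discretion. Protocol 2.3 states: "There is no anticipated therapeutic benefit for the healthy participants in this study".

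**The concern.** The ratio used to size Stage 2 is fixed at 1.05, so what Stage 1 shows about the ratio never enters the decision to continue. A Stage 1 interval lying wholly above 125% or wholly below 80% leads to the same next step as a near miss.

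The branch is easy to reach. With 50 completers, an observed C_max CV above about 29.9% already gives less than 90% power. The planning CV is 30%, and Protocol 4.2 says the C_max variability is not well established.

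What is at stake is the exposure of healthy volunteers: two doses, two residential stays and five outpatient visits each, in a Stage 2 with almost no chance of success.

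**Working it through.** **Inputs.** BE limits 80% to 125%; GMR 1.05; α 0.05 and 0.0294; target power 90% (Protocol 9.4). Stage 1 n = 50; planning CV 30% for C_max and 20% for AUC; Stage 2 sizes 50, 100, 156 and 216 at CV 40%, 50%, 60% and 70%; up to 20% over-enrollment (Protocol 9.5).

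**1. The plan's own figures.** Exact two one-sided tests power for a 2×2 crossover on the log scale, with σ_w = √ln(1 + CV²), SE = σ_w·√(2/N) and N − 2 degrees of freedom:

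- Stage 1, N = 50, α 0.05: 89.8% at CV 30% (stated as approximately 90%).
- Stage 1 plus tabulated Stage 2, α 0.0294: 89.9% to 90.0% at all four CVs. Strictly reaching 90% needs 52, 102, 158 and 218, each 2 more than the table.

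The plan's figures are therefore reproduced. With over-enrollment, 216 × 1.2 ≈ 259.

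**2. When is the Stage 1 90% CI wholly outside the limits?** The half-width is h = t(0.95; 48)·SE = 1.677·SE. The interval is outside when the observed ratio is below 0.80·e^(−h) or above 1.25·e^(h).

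| CV | SE | h | Below | Above |
|---|---|---|---|---|
| 20% (AUC) | 0.0396 | 0.0664 | 0.749 | 1.336 |
| 40% | 0.0771 | 0.1292 | 0.703 | 1.422 |
| 50% | 0.0945 | 0.1585 | 0.683 | 1.465 |
| 70% | 0.1263 | 0.2118 | 0.647 | 1.545 |

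As written, Stage 2 still follows in all these cases if the C_max power check falls short.

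**3. How often would the rule stop the study?** With the variance treated as known, the stop probability for a high ratio is about Φ[(ln GMR − ln upper cut-off)/SE]. At CV 40% and GMR 1.5 this is Φ[(0.4055 − 0.3524)/0.0771] = Φ(0.69) ≈ 0.75, so Stage 2 runs in about 0.25. Simulation of the interim decision (C_max only, n = 50, estimated variance) gives P(Stage 2 runs):

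| True GMR | CV 40%, as written | CV 40%, with rule | CV 70%, as written | CV 70%, with rule |
|---|---|---|---|---|
| 1.25 | 0.96 | 0.91 | 1.00 | 0.95 |
| 1.4 | 0.99 | 0.57 | 1.00 | 0.78 |
| 1.5 | 0.99 | 0.25 | 1.00 | 0.59 |
| 0.65 | 0.99 | 0.16 | 1.00 | 0.51 |

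At GMR 1.25 the fall is about 5 points by construction: a 90% CI lies wholly above its true value in 5% of trials. At GMR 1.5 and 0.65, overall success was at most 0.0002 with or without the rule.

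**4. What does it cost?** Method C was simulated with and without the rule on the same trials (C_max only, n = 50, GMR 1.05). A rule based on the point estimate (stop if the observed GMR is outside 0.80 to 1.25) is shown for contrast.

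| CV | Power lost, CI rule (points) | Power lost, point-estimate rule (points) |
|---|---|---|
| 40% | 0.000 | 0.3 |
| 50% | 0.002 | 1.8 |
| 60% | 0.02 | 4.3 |
| 70% | 0.05 | 7.2 |

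Over GMR 0.85 to 1.05 and CV 30% to 70%, the largest loss with the CI rule is 0.06 points (CV 70%, GMR 0.90). Beyond that range, at GMR 1.05, it is 0.11 points at CV 80%, 0.26 at CV 100%, and 0.11 at CV 70% with 40 completers. A stop for futility can only remove BE declarations, so type I error cannot rise.

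**The case against.** The plan names a two-stage method and applies it consistently in both documents; nothing is contradictory or invalid. A discretionary stop for futility cannot inflate type I error, so the usual reason for insisting on a pre-specified rule is absent. That stands, and it is why this is an improvement and not an error. What a written rule adds is transparency: the sponsor would otherwise decide after seeing unblinded results, with no data monitoring committee.

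A reader might infer that Stage 2 is compulsory, and that 200 or more participants could be dosed after BE has already been ruled out. The documents do not support that reading in three respects.

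- Protocol 10.1.7 allows the sponsor to stop, so the wording describes the algorithm and not an obligation.
- A Stage 2 above 200 needs an observed C_max CV near 70%, against a planning value of 30%. At that CV the rule is at its weakest: Stage 2 would still run in 59% of trials at GMR 1.5 and 51% at 0.65.
- Ruled out means only at 90% confidence on Stage 1. At CV 70% and true GMR 1.05 the rule fires in about 0.14% of trials and loses 0.052 points, so a little over a third of those stopped trials (0.052/0.139) would have passed on pooled data.

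Nothing in the documents points to a ratio as extreme as 1.5 or 0.65, and for moderate differences the gain is small. The 90% CI also differs from the 94.12% CI used for the BE test in this branch. Using the 94.12% interval instead loses at most 0.025 points of power but stops fewer futile studies (64% against 73% at CV 70%, GMR 0.60). Either is defensible.

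**Conclusion.** The gap is real and modest. Both documents let Stage 2 follow a Stage 1 that clearly points to non-equivalence, and the only brake is general sponsor discretion. A CI-based futility stop would close the gap at a power loss of at most about 0.05 points at GMR 1.05.

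That figure assumes at least 50 completers, a C_max CV up to 70% and C_max alone. For AUC at its planned CV of 20%, the cut-off of 1.336 lies about 6 standard errors above a true ratio of 1.05 ((ln 1.336 − ln 1.05)/0.0396 ≈ 6.1), so applying the rule to AUC should add essentially no loss; the overall power with all three parameters was not simulated. AUC is also where the rule is sharpest: at that CV it would fire in about 88% of trials if the true AUC ratio were 1.4, and 95% if it were 0.7.

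The benefit depends on the formulations truly differing by a wide margin. If they are close to equivalent, the rule almost never acts.

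**What to change.** Amend Protocol 9.4 and SAP 10, and the decision figure in each, to read:

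> If BE is not met, Stage 2 will be initiated unless the Stage 1 two-sided 90% CI for the GMR of C_max or either AUC lies entirely below 80% or entirely above 125%, in which case the study stops without concluding BE.

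The cost is one sentence per document plus the power loss given above. The 90% intervals come from the model already fitted at the interim, and the alpha levels do not change. The rule should not be replaced by one on the point estimate, which loses up to about 7 points of power. If far fewer than 50 participants complete Stage 1, or a CV well above 70% is thought plausible, the power loss should be recalculated; it then slightly exceeds 0.1 points.
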